## Division & Personnel

### Division

What Division/Department does the PI belong to?

Substance Abuse

Within the division/department, what Center or group are you affiliated with, if any?

STARS

### Unaffiliated Personnel

List investigators, if any, who will be participating in this protocol but are not affiliated with New York State Psychiatric Institute or Columbia University. Provide: Full Name, Degrees and Affiliation.

None

## Procedures

To create the protocol summary form, first indicate if this research will include any of the following procedures

- Psychiatric Assessment
- Collection of Biological Specimens
- Medication Trial
- MRI

## Population

Indicate which of the following populations will be included in this research

- Adults
- Adults over 50
- Substance Users

## Research Support/Funding

Will an existing internal account be used to support the project?

Yes

Describe internal account

Louis V. Gerstner, Jr., Scholar Award (internal Columbia University Medical Center Award)

Is the project externally funded or is external funding planned?

No

## Study Location

Indicate if the research is/will be conducted at any of the following

- NYSPI

This protocol describes research conducted by the PI at other facilities/locations

No

## Lay Summary of Proposed Research

### Lay Summary of Proposed Research

The overall goal of this project is to combine functional brain imaging and clinical methods in order to examine how treatment with disulfiram (DIS) alters neural activity related to alcohol-seeking motivation in patients with alcohol use disorder (AUD). DIS is an established, effective, FDA-approved medication for AUD that causes a highly aversive visceral reaction if alcohol is consumed while it is being taken. The mere awareness of the risk or threat the DIS-alcohol reaction deters alcohol use, i.e. it is not necessary to drink

alcohol while taking DIS to change behavior. By uncovering the neural mechanisms underlying this risk/threat-based psychological effect, it will be possible to integrate DIS with biologically based treatments targeted at these neural mechanisms, with the goal of improving the efficacy of DIS. Furthermore, the results will shed light on the general neural mechanisms by which awareness of risks of substance use impacts addictive motivation. This is a core process in a number of behavioral treatments for substance use disorders, such as Motivational Interviewing and Contingency Management, as well as in behavior change in non-treatment settings.

## Background, Significance and Rationale

### Background, Significance and Rationale

Disulfiram (DIS) is one of the oldest, most effective, and most commonly used treatments for alcohol use disorder (AUD)(1). DIS is a medication that causes a highly aversive visceral reaction if alcohol is consumed while it is being taken (the DIS-alcohol reaction). Most patients who take DIS do not sample alcohol while taking it (2) indicating that the experience of the DIS-alcohol reaction is not necessary for behavior change, but instead that the mere expectancy or threat of this aversive reaction, i.e. subjective risk, is sufficient to induce behavior change. Here, we are interested in examining the neural underpinnings of this risk-based behavior change mechanism.

The fact that some patients do drink during DIS treatment despite the subjective risk of the DIS-alcohol reaction suggests a limitation of efficacy rooted in a failure of risk-based decision processes. There is a large body of evidence that AUD and other addictive disorders are associated with deficits in risk-based decision making and its neural substrates(3, 4). By understanding the neural mechanisms that mediate behavior change (and the failure of behavior change) during DIS treatment, it may be possible to improve the efficacy of DIS and other treatments that depend upon an awareness of risks by identifying targets for biologically-based augmentation therapies can be combined with such therapies. Such risk-based therapies include DIS, as well as behavioral treatments such as Motivational Interviewing and Contingency Management.

Furthermore, reduction in alcohol use as a result of a shift in subjective risk is likely to play an important role in behavior change outside of treatment.

Previous work by the PI(5) and others(6) has provided circumstantial evidence that excitatory inputs from the insula and the ventromedial prefrontal cortex (VMPFC) into the ventral striatum (VS) drive a specific “goal-directed” form of drug and alcohol seeking that is engaged when there is a high level of subjective risk. The PI has also shown that cue-induced alcohol craving can be reduced by thinking about risks of alcohol use(7). In cigarette smokers, this risk-based form of cognitive regulation of craving is mediated by negative functional connectivity between the dorsolateral prefrontal cortex (DLPFC) and the VS(8). Furthermore, effective AUD treatments consistently down-modulate cue-induced activity in the VS(9), suggesting an important role for this region in therapeutic behavior change.

Based upon this prior work, we propose that DIS treatment - specifically, the mere belief that drinking will cause the DIS-alcohol reaction - changes behavior by promoting a goal-directed mode of cue-induced alcohol seeking. In this mode, the output of the VS is governed by a balance between (1) excitatory inputs from the insula and the VMPFC that together represent the incentive value of alcohol, and (2) inhibitory inputs from the DLPFC that down-modulate VS output according to the perceived unpleasantness and likelihood of the DIS-alcohol reaction. The resulting VS output determines the magnitude of cue-induced craving during DIS treatment, and predicts the likelihood of relapse during DIS treatment.

The goal of this project is to provide pilot data supporting this model by combining clinical DIS treatment with fMRI experiments that probe the neural correlates of alcohol-seeking motivation. The results will represent the first evidence in treatment-seeking AUD patients of a highly novel and clinically relevant model of alcohol seeking motivation and behavior change under specific behavioral contexts that involve high subjective risk and conflict. Because this is a pilot study, it lacks control groups to address certain important confounds. For example, a control group that receives no treatment while still receiving the general supportive elements of the study would control for factors such as the motivation to enter treatment, the effects of general supportive elements, and the mere passage of time; a control group that receives a placebo instead of DIS would control for potential direct CNS effects of DIS, such as effects on dopamine beta hydroxylase. If the pilot study provides a positive signal for the involvement of the proposed circuitry in the mechanism of behavior change during DIS treatment, this will substantiate subsequent, larger, R01-funded studies that will include non-treatment and placebo control groups. The results will also provide specific anatomical targets for future clinical studies that aim to increase the efficacy of DIS and other risk-based behavior interventions by combining them with biological treatments, such as repetitive transcranial magnetic stimulation (rTMS).

An important secondary goal of this study is to examine the neural mechanisms underlying adherence to DIS treatment. There is evidence that adherence to DIS treatment is a major limiter of its effectiveness (10).

Thus, by identifying neural markers that predict adherence during ongoing DIS treatment, as well as markers that predict the decision to continue DIS treatment when there is an option to stop, it may be possible to identify patients who are likely to benefit the most from DIS treatment. Furthermore, these neural markers may also serve as anatomical targets for biological treatments that can be combined with DIS to improve adherence.

## Specific Aims and Hypotheses

### Specific Aims and Hypotheses

We plan to complete data collection in 25 treatment-seeking AUD patients. Following a brief inpatient lead-in phase to facilitate abstinence, the patients will undergo a pre-DIS fMRI scan using a passive alcohol cue-reactivity paradigm, with high-calorie food cues serving as control stimuli. They will then receive 10 days of outpatient open-label DIS treatment that includes taking DIS 500 mg every other day, with supervised dosing. They will then undergo a post-DIS fMRI scan using the same cue-reactivity task used in the pre-DIS scan. They will then be followed for 30 days while receiving open-label DIS 250 mg daily, with weekly medical management visits that will include monitoring of alcohol use and medication adherence, and administering a supervised dose of DIS 250 mg. During both phases, patients will be repeatedly informed of the risk of the DIS-alcohol reaction.

Aim 1: Measuring the effects of DIS treatment on cue-elicited neural activity: We predict that, from the pre- to the post-DIS fMRI scans, there will be: increased cue-induced activity in the insula, VMPFC and DLPFC; increased cue-induced insula-VS positive functional connectivity; increased cue-induced VMPFC-VS positive connectivity; increased cue-induced DLPFC-VS negative functional connectivity; reduced cue-induced activity in the VS; reduced cue-induced craving; and a stronger relationship between cue-induced VS activity and cue-induced craving. These effects of DIS treatment will be specific to alcohol cues. Furthermore, we predict that the effects of DIS treatment on insula-VS and VMPFC-VS functional

connectivity will be mediated by self-report measures of alcohol incentive salience at the post-DIS scan; and that the effects of DIS treatment on DLPFC-VS negative functional connectivity will be mediated by self-report measures of the perceived likelihood and unpleasantness of the DIS-alcohol reaction at the post-DIS scan.

Aim 2: Using the effects of DIS treatment on cue-elicited neural activity to predict relapse: We predict that individual differences in cue-induced VS activity in the post-DIS fMRI scan will predict relapse during a subsequent 30 days of DIS treatment, after controlling for cue-induced VS activity during the pre-DIS scan. Here, relapse will be defined as any alcohol use during the 30-day DIS treatment period.

Secondary Aims: (1) We will identify regions across the whole brain in which the effects of 10-day DIS treatment on cue-induced neural activity predict adherence during 30-day DIS treatment. (2) We will identify regions across the whole brain in which the effects of 10-day treatment on cue-induced neural activity predict the decision to continue DIS treatment beyond 30-days. (3) We will acquire baseline measures of AUD severity, alcohol saliency, motivation for change, impulsivity, self-regulation and tolerance for risk, and will examine how these variables moderate the effects of DIS on cue-induced neural activity. (4) If a significant number ( $>1/3$ ) of patients sample alcohol during the 10-day DIS treatment and thus experience the DIS alcohol reaction, we will perform a subgroup analysis comparing how the neural effects of DIS treatment in such patients differ from patients who do not sample DIS during the 10-day treatment. This will allow us to determine whether the neural effects of actually experiencing the DIS-alcohol reaction are different from the effects of mere expectation of the DIS-alcohol reaction.

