At the end of the 30-day DIS treatment, or at the end of the 30-day extension phase for patients who opt for extending treatment, patients will be offered referrals to a number of outpatient treatment programs where they can receive ongoing treatment for relapse prevention, as well as a list of local Alcoholics Anonymous groups. **At this time, blood will be drawn (10cc, or 2 tablespoons) to assess liver functions and CBC at the end of study.**

MRI Scanning:

Participants will undergo two fMRI scanning sessions at the Center for MRI Research at NYSPI: The first will occur on the last day of the inpatient lead-in phase, just before the first dose of DIS (the pre-DIS MRI scan). The second will occur after the last clinic visit of the 10-day DIS treatment period (the post-DIS MRI scan), which will be approximately 10 days after the first scanning session. The procedures for both fMRI scanning sessions will be largely identical.

Functional MRI scanning sessions at the 3-Tesla Research MRI at NYSPI will be scheduled through the MRI facility website (<http://rfmh.nyspi.org/MRI/>). The process involves viewing the calendar to see available time-slots and reserving open slots as needed. The scanner is open Monday-Sunday from 8am until 8pm. There is a request form on which time-slots are requested. After submitting this form, appointments are confirmed as soon as possible by the Institute. Time-slots generally do not entirely fill up for an entire day, so it is not required to hold a standing reservation for future scanning appointments.

Participants will be instructed to abstain from eating food for 4 hours prior to the scans (they will be allowed to drink non-alcoholic beverages), and to abstain from all drugs of abuse for at least 1 week prior to the scan.

For the pre-DIS scan, participants will be escorted from the inpatient unit to the MRI scanner in the same building at NYSPI by the RA. For the post-DIS scan, patients will be taken via taxi from STARS to the MRI scanner at NYSPI, after completing the clinic procedures for that day.

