Upon arrival at MRI facility, participants will meet with a research assistant, who will administer all of the procedures during the fMRI scan. A physician will not be present for the MRI scans, consistent with usual MRI center policies for scans that do not involve contrast agents or medications being administered during the scans. Participants will be screened for metallic devices and implants using a metal detector (a self-report screening will have occurred prior to enrollment). The urine sample obtained at the STARS clinic will have been tested for pregnancy. Participants will be administered the Alcohol Craving Questionnaire (ACQ) to assess the current level of alcohol craving, the Food Craving Questionnaire (FCQ) to assess the current level of food craving/hunger. The scanning procedure will be reviewed and the participant will be free to ask questions prior to the scan.

During each of the scans, participants will undergo the Cue Exposure task (20 minutes). This is a previously validated passive cue-exposure task that involves showing the participants pictures of alcohol and food cues in randomized order, and then asking them to rate their desire to consume the depicted item on a 1-5 Likert scale after each cue. The Cue-Exposure task is expected to increase cravings for alcohol and food, and the analysis of brain activity will focus on how DIS treatment changes cue-induced craving and cue-induced neural activity in response to alcohol and food cues, respectively. Additionally, participants will undergo a resting fMRI scan (10 minutes) and an anatomical MRI scan (5 minutes).

Following each scan, patients will complete the DIS-Risk questionnaire to assess for the level of belief that alcohol use will lead to the DIS-alcohol reaction.

The MRI scanning procedure will take approximately 1.5 hour, including 1 hour within the scanner. Participants will be paid \$50 for the first fMRI scanning session and \$100 for the second fMRI scanning session, whether or not they complete the scanning procedures.

You can upload charts or diagrams if any  
Ativan taper schedules.pdf  
Instructions to patients taking disulfiram.pdf

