## Assessment Instruments

Create a table or give a brief description of the instruments that will be used for assessment

At screening, the RA will administer a 30-day Timeline Followback (TLFB) to quantify alcohol use and will include the Montreal Cognitive Assessment (MOCA) to assess cognitive functioning. The psychotherapist will administer the Mini International Neuropsychiatric Instrument (MINI) to diagnose Alcohol Use Disorder and other psychiatric disorders. The psychiatrist will administer a psychiatric evaluation; the Hamilton Depression Inventory (HAM-D); the Hamilton Anxiety Inventory (HAM-A); the Clinical Institute for Withdrawal Assessment - Revised (CIWA-Ar); the Clinical Global Impression Scale (CGI); and the Treatment Services Review (TSR).

During the inpatient admission the patients will complete the following self-report questionnaires: The Barratt Impulsiveness Scale (BIS) will assess the level of trait impulsivity. The Alcohol Dependence Scale (ADS) will assess the severity of Alcohol Use Disorder. The Obsessive Compulsive Drinking Scale (OCDS) will assess the level of alcohol incentive salience. The Readiness to Change Questionnaire (RCQ) will assess the motivation to reduce drinking. The Alcohol Abstinence Self-Efficacy Scale (AASE) will assess the level of self-regulation of alcohol-seeking motivation. The Drinker Inventory of Consequences (DrInC) will assess prior experiences with negative consequences from alcohol. The Domain Specific Risk Taking Scale (DOSPERT) will assess the level of risk aversion/preference in a variety of domains. The DIS-Risk scale will ask two questions rating the perceived likelihood and unpleasantness of the DIS-alcohol reaction.

The OCDS, RCQ, AASE will be repeated on the last day of the 10-day DIS treatment, at the STARS clinic, prior to the post-DIS MRI scanning session. The ACQ, FCQ and the DIS-Risk will be administered right before the MRI scans.

Citations for these instruments, as well as the schedule for administration, may be found in the section "Assessments".

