The DIS-Risk is the only non-standard instrument. It comprises the following two items: (1) "How certain are you that drinking alcohol today would result in an unpleasant physical reaction?" (1 = "I am completely certain that I will not have any reaction"; 10 = "I am completely certain that I will have a reaction") and (2) "Assuming that this reaction will happen, how unpleasant/painful do you think it will feel?" (1 = "It won't be unpleasant at all;" 10 = "It will be the most painful feeling I have ever had").

Please attach copies, unless standard instruments are used  
Assessments.pdf

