Study: # 7193 entitled NEUROCOGNITIVE MECHANISMS OF DISULFIRAM TREATMENT OF ALCOHOL USE DISORDER

PI: [name], PhD

NCT# NCT02735577

Data Analysis Plan created: November 14, 2014

Data Analysis: Functional images will be pre-processed according to standard procedures. A whole-brain general linear model analysis will examine effects of time-point (pre-DIS vs. post-DIS) and cue-type (alcohol vs. food), as well as interaction effects. Psychophysiological interaction analysis will examine cue-elicited functional connectivity between the VS and its inputs from the insula, VMPFC and DLPFC, and how these are changed from pre- to post-DIS. Statistical mediation analyses will determine the extent to which these changes are mediated by the perceived likelihood and salience of the DIS alcohol reaction. Logistic regression analysis will be used to determine whether post-DIS cue-induced VS activity predicts drinking during 1 month of DIS, after controlling for pre-DIS cue-induced VS activity, as well as for AUD severity, motivation, risk-taking, insight and impulsivity.

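### Aim 1 ties mediation of a pre-to-post connectivity change to post-DIS self-report scores, and the SAP states neither the mediator time-point nor how baseline is handled

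*Protocol*

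**What the plan says.** Aim 1 (Protocol, Specific Aims and Hypotheses) predicts changes in connectivity from the pre-DIS to the post-DIS scan and names mediators for them. Effects on insula-VS and VMPFC-VS connectivity "will be mediated by self-report measures of alcohol incentive salience at the post-DIS scan". Effects on DLPFC-VS connectivity will be "mediated by self-report measures of the perceived likelihood and unpleasantness of the DIS-alcohol reaction at the post-DIS scan".

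The SAP has one sentence on this. It will determine how far "these changes are mediated by the perceived likelihood and salience of the DIS alcohol reaction". It gives no time-point, baseline handling, model or test of the indirect effect.

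The instruments are under Assessment Instruments. "The Obsessive Compulsive Drinking Scale (OCDS) will assess the level of alcohol incentive salience"; it is completed during the inpatient admission and repeated on the last day of the 10-day treatment. The DIS-Risk has two items, certainty of a reaction and its unpleasantness ("Assuming that this reaction will happen, how unpleasant/painful do you think it will feel"). On its timing the protocol says both "The ACQ, FCQ and the DIS-Risk will be administered right before the MRI scans" (Assessment Instruments) and "Following each scan, patients will complete the DIS-Risk questionnaire" (MRI Scanning). The first scan is "just before the first dose of DIS (the pre-DIS MRI scan").

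**The concern.** A mediation claim needs two links: treatment moves the mediator, and movement in the mediator goes with movement in the outcome. With a single arm, the first link is the mean change in the mediator, which needs the pre-DIS score. The second link is also exposed if only the post-DIS score is used. People who always score high on salience, or always expect bad reactions, may differ in how their connectivity changes. That stable difference would then look like mediation.

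Mediation is the part of Aim 1 that connects self-reported salience and perceived risk to the circuit changes, so a trait correlate could be read as a mechanism. An analyst who followed the SAP as written would also leave the predicted insula-VS and VMPFC-VS mediation untested, because the mediator named for those pathways is not in it.

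**Working it through.** **The texts side by side**

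| Item | Aim 1 | SAP |
|---|---|---|
| Mediator, insula-VS and VMPFC-VS | Alcohol incentive salience | Not named |
| Mediator, DLPFC-VS | Likelihood and unpleasantness of the reaction | Likelihood and salience of the reaction, not tied to a pathway |
| Mediator time-point | Post-DIS scan | None |
| Role of pre-DIS mediator score | None | None |

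For Aim 2, the same protocol section states adjustment for the pre-DIS scan explicitly. Secondary Aim 3 uses baseline alcohol saliency, but as a moderator of neural activity.

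**Inputs.** The plan gives no figure for this analysis, so there is none to reproduce. n = 25 completers comes from the protocol. Everything else is assumed: two-sided 0.05; equal pre and post SD; test-retest correlation r = 0.5-0.8; a stable trait correlated ρ = 0.3-0.5 with connectivity change; mediator mean shift δ = 0, 0.5 or 0.8 SD of change. The trait is not a mediator here, so every detection is false.

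**First path (mean change).** Noncentrality is δ√n: 0.5 × 5 = 2.5 (power 0.67) and 0.8 × 5 = 4.0 (power 0.97). At δ = 0 the rate is 0.05.

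**Second path, post score only.** The correlation with connectivity change is ρ√r, from 0.3 × √0.5 = 0.21 to 0.5 × √0.8 = 0.45. Simulated rejection is 17.2% to 63.6%. Requiring the first path as well:
- δ = 0.5-0.8: 0.172 × 0.67 = 0.115 up to 0.636 × 0.97 = 0.617. Simulated jointly: 11-61%.
- δ = 0: 0.05 × 0.172 = 0.009 up to 0.05 × 0.636 = 0.032. Simulated jointly: 0.9-3.1%.

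**Second path, post adjusted for pre.** The partial correlation is ρ√r(1−r) / √[(1−ρ²r)(1−r²)]. It is 0.093 at ρ = 0.3, r = 0.8 and 0.218 at ρ = 0.5, r = 0.5. By Fisher's z with √21, rejection is about 7% and 17%. With the first path: 0.07 × 0.67 = 0.05 and 0.17 × 0.97 = 0.16. Simulated: 5-17%. It is not zero because the pre score measures the trait with error.

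**Second path, change adjusted for the pre/post mean.** With equal SDs, change is uncorrelated with the trait, so the slope rejects at 5%: 0.05 × 0.67 = 0.034 and 0.05 × 0.97 = 0.049. Simulated: 3-5%.

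**Power, equal SDs, correlation 0.50**
- If connectivity change follows the mediator's change, the post-only slope detects 12-23% and change adjusted for the mean (both paths) 47-71%.
- If it follows the post score alone, the post-only slope detects 75%, or 0.75 × 0.67 = 0.50 to 0.75 × 0.97 = 0.73 with the first path required. Post adjusted for pre (both paths) detects 23-59%, and change adjusted for the mean (both paths) 9-26%.

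**DIS-Risk-like scores.** Assume pre-dose SD 25-50% of post SD, r = 0.3-0.7 and δ = 1.5. The first path is then nearly always passed, since 1.5 × 5 = 7.5.

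| Second path | Trait flagged | True change effect detected |
|---|---|---|
| Post only | 12-57% | 60-73% |
| Post adjusted for pre | 8-17% | 59-73% |
| Change adjusted for mean | 5-10% | 15-54% |

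**Timing.** The two statements on DIS-Risk order cannot both hold. The first OCDS belongs to the admission (Inpatient Lead-In Phase puts the self-reports on day 1 or 2), while the pre-DIS scan is on the day of discharge. OCDS change therefore also spans inpatient abstinence. The Assessments upload was not available and may settle OCDS timing; the conflict within the protocol text on DIS-Risk remains.

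**The case against.** **No document commits to a post-only analysis.** This stands. Aim 1 is a hypothesis, the SAP is silent on timing, and both instruments are collected before and after DIS. A reader might infer that the plan will run a post-only model with a 17-64% error rate. The documents do not say so; those figures describe one analysis that the wording permits. What remains is that no text brings the pre-DIS score into the mediation.

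**Setting 17-64% against a fraction of a percent is uneven.** This also stands. The first range needs one significant test. A two-wave joint rate of about 0.3% (0.05 × 0.05 = 0.0025 with no mean change) needs two. Any proper mediation analysis tests the first path, and that test alone removes most of the problem when the mediator mean does not move. It does not when the mean moves.

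**No single model is clearly best.** Agreed. Adjusting for the mean protects better against a trait, but costs power if the post score is what matters, and for DIS-Risk-like scores. Prior disulfiram treatment is an exclusion and the first scan precedes dosing, so pre-DIS certainty of a reaction may sit near its floor and the post score would approximate the change. That is an assumption, and it does not help the OCDS.

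**It is an acknowledged pilot.** The Background section concedes the missing control groups. It does not address stable differences between people passing as mediation. Its criterion for larger studies is a signal for the circuitry, though, so it would be too strong to say that those studies hinge on the mediation result.

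**Conclusion.** The point holds as a gap in specification, at the low end of should-fix. Aim 1 attaches mediation to post-DIS scores, which cannot carry the treatment-to-mediator path in a single-arm design. The SAP does not repair this and lacks the mediator for two of the three pathways.

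Its size is illustrative, because every effect is assumed. If the mediator mean shifts by 0.5-0.8 SD of change, false mediation from a stable trait is about 11-61% with the post score, against 5-17% or 3-5% when the pre-DIS score is used. If the mean does not shift, the post-score rate is 0.9-3.1% and little is at stake.

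Two further inferences are not supported. The SAP did not drop the pairing of mediators with pathways: it is dated November 2014, while the protocol cites a source accessed in July 2015 and lists a January 2016 consent file. The pre-DIS scores are also neither missing nor unused, since baseline salience has a moderator role in Secondary Aim 3.

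**What to change.** In the SAP and Aim 1:

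1. Use both the pre-DIS and post-DIS mediator scores. Estimate the mean change as the first path and include the pre-DIS score in the second, either as post adjusted for pre or as change adjusted for the pre/post mean. Name one in advance, report the other as a sensitivity analysis, and give an interval for the indirect effect.
2. Name the OCDS as mediator for insula-VS and VMPFC-VS, and the two DIS-Risk items (likelihood, unpleasantness) for DLPFC-VS.
3. Reconcile MRI Scanning with Assessment Instruments on whether the DIS-Risk comes before or after the scan, and keep the same order at both scans.
4. State that the first OCDS precedes the pre-DIS scan, so its change also covers inpatient abstinence.
5. Label the analysis exploratory and non-causal. If only post-DIS scores are used, or an item's pre-DIS scores do not vary, call the result an association.

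The cost is wording in two documents; no new data are needed. The statistical price is some loss of power if only the post-DIS score matters, and more measurement error in change scores. DIS and the passage of time stay inseparable, as the protocol already acknowledges.
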